15.5 Vital Signs

The maximum change (increase and decrease) in each vital sign measurement from baseline (where baseline is defined in Section 9.4) across on-treatment scheduled and unscheduled visits performed during Period 1 will be derived, as shown below for each participant. See Section 9.3 for the definition of on-treatment periods.

Body temperature increase < 37 °C, ≥ 37 - < 38 °C, ≥ 38 - < 39 °C, ≥ 39 - < 40 °C, ≥ 40 °C	$< 1 ^{\circ}C, 1 -< 2 ^{\circ}C, 2 -< 3 ^{\circ}C, \ge 3 ^{\circ}C$
Pulse increase from baseline < 100 bpm; ≥ 100 bpm	≤ 20 bpm, $> 20-40$ bpm, > 40 bpm
Pulse decrease from baseline < 100 bpm; ≥ 100 bpm	≤ 20 bpm, $> 20-40$ bpm, > 40 bpm
SBP increase from baseline < 140 mmHg; ≥ 140 mmHg	\leq 20 mmHg, $>$ 20 – \leq 40 mmHg, $>$ 40 mmHg
SBP decrease from baseline < 140 mmHg; ≥ 140 mmHg	\leq 20 mmHg, $>$ 20 – \leq 40 mmHg, $>$ 40 mmHg
DBP increase from baseline < 90 mmHg; ≥ 90 mmHg	\leq 20 mmHg, $>$ 20 – \leq 40 mmHg, $>$ 40 mmHg
DBP decrease from baseline < 90 mmHg; ≥ 90 mmHg	\leq 20 mmHg, $>$ 20 – \leq 40 mmHg, $>$ 40 mmHg
Respiration rate increase from baseline < 20 bpm; ≥ 20 bpm	≤ 5 bpm, $>5-\leq 10$ bpm, >10 bpm
Respiration rate decrease from baseline < 20 bpm; ≥ 20 bpm	≤ 5 bpm, $> 5 - \leq 10$ bpm, > 10 bpm

The number and percentage of participants in each category will be presented as a shift table showing baseline category versus the maximum change. The denominator to calculate percentages for each vital sign parameter is the number of participants in each analyzed group. Participants without baseline or post-baseline results for a given parameter will be presented in the "Missing" category and will contribute to the denominator.

For body weight, the number and percentage of participants with a maximum on-treatment percent change from baseline increase and decrease will be presented. Categories will be: < 10%, $\ge 10\%$ and missing. Those participants with no baseline and/or post-baseline measurement will be presented in the "Missing" category.

A participant data listing will present the baseline and maximum changes (increases and decreases) in each vital sign measurement. A listing presenting all vital sign measurements will also be produced. A flag will be used to indicate which measurements belong to the on-treatment periods.

15.6 Other Safety or Tolerability Evaluations

15.6.1 ECOG Performance Status

ECOG Performance Status information is collected on the "ECOG Performance Status" eCRF page.

ECOG Performance Status will be summarized using shift tables showing baseline versus minimum and maximum on-treatment values. Participants without baseline or on-treatment results from Period 1 will be presented in the "Missing" category and will contribute to the denominator. See Section 9.3 for the definition of on-treatment periods.

Listings of each participant's ECOG Performance Status over time will be provided. A flag will be used to indicate which measurements belong to the on-treatment periods.

15.6.2 Electrocardiogram (ECG)

Single 12-lead ECG will be obtained using an ECG machine that automatically calculates the heart rate and measures PR, QRS, QT and QTcF intervals. Electrocardiogram (ECG) results will be read locally and only one reading per visit will be performed.

For each of the ECG parameters (HR and QT, derived QTcF, QRS, PR intervals), descriptive statistics at baseline, at each on-treatment time point and changes from baseline at each on-treatment time point for scheduled visits will be presented. In addition, with the exception of the baseline, end of treatment and safety follow-up visits, all the other visits will be presented if the data are available for at least 6 participants overall.

The ECG assessment [Normal, Abnormal (not clinically significant), Abnormal (clinically significant)] will be presented as a shift table showing baseline versus the worst on-treatment result measured during Period 1. See Section 9.3 for the definition of on-treatment periods.

The change in QT interval corrected for the heart rate by the Fridericia's formula (i.e., QTcF) between baseline and the worst (maximum) on-treatment result will be summarized in shift tables as follows:

• Categorical shift from baseline to worst on-treatment value for the QTcF:

Parameter	Baseline category	Worst on-treatment value
QTc (Fridericia)	\leq 450 ms	\leq 450 ms
	> 450 ms > 450 ms	
	> 480 ms > 480 ms	
	> 500 ms	> 500 ms

Parameter	Baseline category	Worst change from baseline
QTc (Fridericia)	\leq 450 ms	\leq 30 ms
	> 450 ms	> 30 ms
	> 480 ms	> 60 ms
	> 500 ms	

• Categorical shift from baseline to worst on-treatment change from baseline for the QTcF:

The QTcF will be collected in the eCRF page; if the ECG machine only provides the QT interval corrected with the Bazett formula (QTcB), the eCRF will automatically calculate the QTcF. If both QTcF and QTcB values are reported in the eCRF, two QTcF values will be available. In this case, only the QTcF and QTcB values reported by the Investigator in the eCRF will be listed.

For analysis purposes, the QTcF value will be derived as:

$$QTcF(msec) = \frac{QT(msec)}{\sqrt[3]{\frac{60}{HR(beats/min)}}}$$

The derived QTcF will be presented in the summary table, listed and used for the shift tables described above.

Unscheduled ECG measurements will not be used in computing the descriptive statistics for change from baseline at each post-baseline time point. However, they will be used in the derivation of worst on-treatment values.

Listings of all participants ECG results will be presented. A flag will be used to indicate which measurements belong to the on-treatment periods.

Echocardiogram results from measurements performed at screening and at the end of treatment visit will also be listed.

16 Analyses of Other Endpoints

16.1 Pharmacokinetics

16.1.1 Concentration Data

Tepotinib and metabolite (MSC2571109A and MSC2571107A), and osimertinib and metabolite (AZD5104) concentrations in plasma will be listed and presented in tables, and descriptively summarized by treatment, day, and scheduled time point. For calculation of descriptive statistics of concentration data, values that are below the limit of quantification (i.e., BLQ; values that are below the lower limit of quantification [LLOQ]) will be set to zero. Descriptive summary tables and data listings will be prepared separately for the Rich PK Sampling subjects (i.e., Safety Runin subjects) and the Sparse PK Sampling subjects. Pharmacokinetic concentrations will be

summarized by PK analyte, treatment arm (for Sparse PK Sampling subjects only), cycle/day, and nominal time, as described in Section 8.

The following plots will be prepared for the Rich PK Sampling Subject group:

- By-participant plots: Individual (i.e., by- participant) plasma concentration-time plots (one plot per participant, with both days overlaid) will be plotted separately by analyte (i.e., tepotinib, MSC2571109A, MSC2571107A, osimertinib, and AZD5104) on linear and semi-logarithmic scales using actual time points.
- Spaghetti plots: Spaghetti plots overlaying all participants' concentration-time profiles (linear and semi-logarithmic scales) will be plotted by day for each of the 5 analytes separately (i.e., tepotinib, MSC2571109A, MSC2571107A, osimertinib, and AZD5104) using actual time points.
- Mean plots: Mean plasma concentration time plots with both days overlaid will be plotted separately by analyte (i.e., tepotinib, MSC2571109A, MSC2571107A, osimertinib, and AZD5104) on linear (±StDev) and semi-logarithmic scales using scheduled time points.

A listing of PK blood sample collection times by individual as well as derived sampling deviations will be provided for all subjects with collected PK data. Data excluded from the PK analysis set will be flagged, along with the reason for exclusion.

The PK data from this study will also be analyzed jointly with data from other tepotinib studies using a non-linear mixed effect approach. The details of this population PK analysis will be described in a separate Data Analysis Plan, and results will be reported separately.

16.1.2 Pharmacokinetic Parameters

The computer program Phoenix® WinNonlin® version 6.4, or higher (Certara, L.P., [name]) will be used to derive PK parameters applying Non-compartmental analysis (NCA).

The statistical software SAS® (Statistical Analysis System, SAS-Institute, Cary NC, USA, windows version 9.4 or higher) may be used to generate additional PK parameters, produce tables, listings and figures.

For participants in the Rich PK Sampling group (i.e., Safety Run-in subjects), PK parameters will be calculated using standard non-compartmental methods. Actual elapsed sampling times and the actual administered dose will be used for calculation of parameters for the final analysis (after database lock). For SMC meetings or IDMC meetings, nominal times and doses will be used for calculation.. The PK parameters listed below will be calculated for tepotinib and metabolites (MSC2571109A and MSC2571107A) and for osimertinib and its metabolite (AZD5104) in plasma, when applicable.

 C_{max}

Maximum observed concentration

t _{max}	Time of C _{max}
AUC _{0-t}	Area under the concentration-time curve from time zero to the last quantifiable concentration
AUC ₀₋₁₂	Area under the concentration-time curve over the dosing interval from $T_1=0$ h (predose) to $T_2=12$ h. Calculated using the mixed log linear trapezoidal rule (linear up, log down). AUC ₀₋₁₂ on both Day 1 and Day 15 of Cycle 1 will be calculated as a partial area within the defined time range. If there is a time deviation at the 12-hour time point or the concentration is missing, the AUC will be interpolated to 12 hours.
t _{lag}	Time prior to the first quantifiable (non-zero) concentration (for Cycle 1 Day 1 only)
C_{av}	Average concentration at steady state, calculated on Cycle 1 Day 15 only. $C_{av} = AUC_{\tau} / \tau$ (AUC _{0-t} if necessary).
C _{min}	Minimum observed concentration during a complete dosing interval, calculated on Cycle 1 Day 15 only.
ΑUCτ	Area under the concentration-time curve over the dosing interval from $T_1=0$ h (predose) to $T_2=\tau$ h. Since the dosing interval τ is equal to 24 hours in this study, this parameter is equivalent to AUC ₀₋₂₄ (area under the concentration-time curve from $T_1=0$ h [predose] to $T_2=24$ h) on both Day 1 and Day 15 of Cycle 1. Calculated using the mixed log linear trapezoidal rule (linear up, log down). For Cycle 1 Day 1, AUC _{τ} will be calculated as a partial area within the defined time range. For Cycle 1 Day 15, AUC _{τ} will be calculated at steady state from the pre-dose time point to the dosing interval time. AUC _{τ} will be calculated based on the observed concentration at the actual observation time, as long as actual time deviation is less than +/-10% at τ . If actual time deviation is equal to or greater than 10%, AUC _{τ} will be reported as missing.
CL/F	Apparent systemic clearance (calculated for tepotinib and osimertinib only), as Dose/AUC _{τ} . Calculated on Cycle 1 Day 15 only. For tepotinib, Dose is the tepotinib free base dose (i.e., adjusted for salt form). The tepotinib free base dose is calculated as: Actual dose × MW(free base)/MW(salt), where MW(free base) is the molecular weight (MW) of free base (i.e., 492.57), and MW(salt) is the MW of the
	CONFIDENTIAL 83/94

	hydrochloride hydrate salt (i.e., 547.05). For osimertinib, the dose administered is the free base form, so no dose adjustment is required.			
AUC _{0-t} /Dose	Dose-Normalized AUC _{0-t} (calculated for tepotinib only). Normalized using actual dose (i.e., unadjusted for salt form).			
AUC ₀₋₁₂ /Dose	Dose-Normalized AUC_{0-12} (calculated for tepotinib only). Normalized using actual dose (i.e., unadjusted for salt form).			
AUC _t /Dose	Dose-Normalized AUC _{τ} (calculated for tepotinib only). This parameter is equivalent to AUC ₀₋₂₄ /Dose. Normalized using actual dose (i.e., unadjusted for salt form).			
C _{max} /Dose	Dose-Normalized C_{max} (calculated for tepotinib only). Normalized using actual dose (i.e., unadjusted for salt form).			
PTF	Peak trough fluctuation ratio within a complete dosing interval at steady state in %, calculated on Cycle 1 Day 15 only. $PTF = 100*(C_{max}-C_{min})/C_{av}$			

Potential drug accumulation for tepotinib and its metabolites and for osimertinib and its metabolite will be evaluated by means of individual accumulation ratios for AUC_{τ} and C_{max} (R_{acc(AUC)} and R_{acc(Cmax)} respectively), that will be calculated by dividing the values obtained after multiple dose (i.e., on Cycle 1 Day 15) by the values obtained after single dose (i.e., Cycle 1 Day1) and summarized descriptively for each dose level.

Individual metabolite to parent ratios for AUC_{τ} and C_{max} (MR_(AUC) and MR_(Cmax), respectively), will be calculated for tepotinib and its metabolites by dividing the value obtained for each metabolite by the value obtained for the parent (i.e., MSC2571107A/tepotinib) and MSC2571109A/tepotinib) after correction for MW differences between parent and metabolite (MW of tepotinib free base is 492.57, MW of MSC2571107A is 506.56, and MW of MSC2571109A is 506.56), separately for single dose (i.e., Cycle 1 Day 1) and multiple dose (i.e., Cycle 1 Day 15), and summarized descriptively for each dose level and day. Similarly, metabolite to parent ratios for AUC_{τ} and C_{max} will be calculated for osimertinib and its metabolite by dividing the value obtained for the metabolite by the value obtained for the parent (i.e., AZD5104/osimertinib) after correction for MW differences between parent and metabolite (MW of osimertinib free base is 499.6 and MW of AZD5104 is 485.6).

The dosing and sampling scheme in this study does not allow the reliable estimation of λ_z , considering the apparent terminal half-life of tepotinib and its metabolites, and osimertinib and its metabolite. Therefore, any PK parameters dependent on λ_z will not be determined, i.e., AUC_{0-∞} (single dose), CL/F (single dose), and V_Z/F (single and multiple dose).

Other parameters may be added as appropriate.

The calculation of the AUCs will be performed using the mixed log-linear trapezoidal method (linear up, log down). The actual (unrounded) time of blood sampling will be used for PK evaluation. In cases where the actual sampling time is missing, calculations will be performed using the scheduled time. Otherwise, there will be no further imputation of missing data. The pre-dose samples will be considered as if they had been taken simultaneously with the administration. Plasma concentrations below LLOQ before the last quantifiable data point will be taken as zero for calculating the AUC (i.e., embedded BLQ values will be set to zero). Plasma concentrations below LLOQ after the last quantifiable data point will be set to 'zero'.

PK parameters will be evaluated and listed for all participants who provide sufficient concentration-time data. Data excluded from the PK analysis set will be flagged, along with the reason for exclusion. Pharmacokinetic parameters will be rounded for reporting as appropriate. In export datasets, PK parameters will be provided with full precision, and will not be rounded. PK parameters will be summarized by PK analyte, and cycle/day, as described in Section 0.

Formal statistical hypotheses have not been planned for PK parameters. Any statistical tests that might be performed will be considered exploratory.

The Phoenix WinNonlin NCA Core Output will be provided in a separate listing.

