4.1 Overall Design

This Phase II, two-arm, open-label study will assess the antitumor activity, safety, tolerability, and PK of the MET inhibitor tepotinib alone and combined with the 3rd generation EGFR inhibitor osimertinib in participants with advanced or metastatic NSCLC harboring activating EGFR mutations and having relapsed on prior first-line osimertinib due to MET amplification.

Prescreening

After written informed consent for Prescreening procedures has been obtained, MET amplification status will be centrally assessed by fluorescence in situ hybridization (FISH) or by reviewing pre-existing local FISH results using tumor tissue (TBx), and centrally by blood-based next generation sequencing (LBx). Biospecimens for TBx (central and local) and LBx prescreening must be collected after documented relapse of participants with EGFRm⁺ NSCLC on previous first-line osimertinib treatment.

Participants with MET amplification detected locally by FISH are required to sign the Prescreening informed consent form (ICF) and provide the information on the results and the local FISH assay used. Those participants must also provide blood for the central LBx testing after signing prescreening ICF (Section 8.8).

In case of administrative, operational or logistical errors, insufficient TBx material available/provided from previous local FISH testing or if the provided TBx or LBx sample could not be evaluated at the testing laboratory, repeat collections of TBx and/or LBx may be performed without the need to obtain a new written informed consent for Prescreening.

Participants who were identified MET amplification positive and who had progressed on previous first-line osimertinib are recommended to continue treatment with osimertinib beyond progression, at the discretion of the Investigators, also in line with current clinical guidelines ([NCCN Version 3, 2019](#)) and criteria as defined by [Jackman 2010](#), until they either receive the experimental treatment as defined in this study, or in the case of ineligibility, a follow-up treatment as discussed with their physician.

Screening Period

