Next to EGFR-related resistance, MET gene amplification constitutes the most frequent cause of bypass pathway activation as an acquired resistance mechanism to EGFR TKIs (Wu 2017; Papadimitrakopoulou 2018; Ramalingam 2018). When osimertinib was given as a first-line therapy, MET amplification was the most common resistance mechanism, encountered in 15% of patients by next generation sequence circulating tumor DNA (ctDNA) analysis. Moreover, this percentage is expected to be higher in tissue, due to the underestimation of gene amplification in plasma (Leonetti 2019; Ramalingam 2018).

Activated MET thereby acts as a secondary oncogenic driver in EGFRm+ NSCLC, requiring the concurrent inhibition of both MET and EGFR (Engelman 2007; Turke 2010). Therefore, INSIGHT 2 investigates concomitant inhibition of both targets with the combination of the highly selective MET inhibitor tepotinib and osimertinib, in patients with EGFRm+ and MET amplified, locally advanced or metastatic NSCLC who have progressed on first-line osimertinib. It will also assess the contribution of tepotinib to the osimertinib and tepotinib combination therapy in the same population but no formal statistical comparison between the combination arm and the monotherapy arm is planned.

The strong addiction on the EGFR pathway is also demonstrated by 2 clinical phenomena observed in subsets of EGFRm+ NSCLC patients. A disease flare was seen in patients having discontinued their EGFR inhibitor treatment after relapse (Chafit 2011). Moreover, single responses were noted in patients following wash-out and re-start of EGFR TKI treatment after previous relapse on EGFR TKIs (Cappuzzo 2016). Therefore, patients who are identified as MET amplification positive and who had documented progression on previous EGFR TKI treatment are recommended to continue treatment with the EGFR TKI beyond progression in line with current clinical guidelines (NCCN version 3, 2019) and criteria as defined by Jackman 2010 until they either receive the experimental treatment as defined in this study, or in the case of non-eligibility, a follow-up treatment as discussed with their physician.

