Appendix 2 Study Governance

Financial Disclosure

Investigators and Sub-Investigators will provide the Sponsor with sufficient, accurate financial information, as requested, for the Sponsor to submit complete and accurate financial certification or disclosure statements to the appropriate regulatory authorities. This information is required during the study and for 1 year after completion of the study.

Informed Consent Process

- To enroll in this study, participants will first need to sign a Prescreening informed consent form (ICF). Once signed, Mesenchymal-epithelial Transition Factor (MET) amplification status will be assessed by liquid biopsy. Participants with positive MET amplification and who had progressed on epidermal growth factor receptor (EGFR) tyrosine kinase inhibitor (TKI) treatment should continue with the EGFR TKI beyond progression, until they either receive the experimental treatment as defined in this study or in the case of ineligibility, a follow-up treatment as discussed with their physician. In case of eligibility, participants should sign a second ICF at Screening.
- The Investigator or his/her representative will explain the nature of the study to the participant and answer all questions on the study.
- Participants must be informed that their participation is voluntary.
- Participants will be required to sign a statement of informed consent that meets the requirements of 21 CFR 50; the Japanese ministerial ordinance on Good Clinical Practice (GCP); local regulations; ICH guidelines; Health Insurance Portability and Accountability Act (HIPAA) requirements, where applicable; and the IRB/IEC or study center.
- The medical record must include a statement that written informed consent was obtained before the participant was enrolled in the study and the date the written consent was obtained. The authorized person obtaining the informed consent must also sign the ICF.
- If the ICF is updated during their participation in the study, participants must be re-consented to the most current, approved version.
- A copy of the ICF(s) must be provided to the participant.
- The original signed and dated consent will remain at the Investigator's site and must be safely archived so that it can be retrieved at any time for monitoring, auditing, and inspection purposes.
- Participants who are rescreened are required to sign a new ICF.

Data Protection

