The SRIAS will include all participants treated in the safety run-in who received at least 75% of the tepotinib and osimertinib planned dose and completed the DLT period (3 weeks after start of treatment with study treatment), or who experienced a DLT during the DLT period regardless of the received amount of each study treatment.

Planned tepotinib dose: $500 \text{ mg} \times 21 \text{ days} = 10500 \text{ mg}.$

Planned osimertinib dose: $80 \text{ mg} \times 21 \text{ days} = 1680 \text{ mg}.$

DLTs are identified as those AEs with answer "Yes" to the question "Is this adverse event a dose limiting toxicity", which is collected on the "Adverse Event Details" eCRF page. The respective eCRF flag will reflect the decisions of the SMC regarding the assessment of an adverse event being a DLT.

Pharmacokinetic Analysis Set (PKAS)

All participants who receive at least one dose of study treatment, have no important events or protocol deviations affecting PK and provide at least one measurable post-dose concentration.

The PKAS will include all participants:

• Who have PK data without any relevant protocol deviations and factors likely to affect the validity of these data

• With adequate study treatment compliance (i.e., dosing and dosing regimen is as scheduled on the PK measurement day(s), as well as on prior days which have the potential to impact PK results).

• With evaluable PK data, i.e., non-missing values sufficient to derive PK endpoints.

If participants received prohibited concomitant therapy or medicines, as specified in Section 6.5 of the protocol (refer to clinical study protocol MS200095-0031), they will be excluded from the PKAS. Relevant decisions will be made before database lock.

Additionally, the following will be considered for inclusion in the PKAS: if a participant has a tepotinib dose change, the affected PK data (for both tepotinib and osimertinib treatment) will no longer be included in the PKAS from the time of the change.

If there is a change in scheduled osimertinib dose which can affect osimertinib PK (e.g., inadequate washout of prior osimertinib treatment or missed osimertinib doses), the affected osimertinib concentrations and/or PK parameters will be excluded from the PKAS.

All PK summaries will be based on the PKAS population.

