9.2 Study Day / Study Treatment Day

In this IAP, "study treatment" comprises tepotinib and osimertinib in the combination arm and indicates tepotinib only in the monotherapy arm; "study treatment component" will be used to refer to each study drug separately.

Day 1 is the day of the start of study treatment, the day before is Day -1 (no Day 0 is defined). Study day / Study treatment day is defined relative to Day 1.

Study treatment start date:

For each participant, the study treatment start date is the date of first administration of the study treatment (for the combination arm, it will be the earliest date between the two study treatment components; for the monotherapy arm it will be the date of the first administration of tepotinib).

Study treatment end date:

For each participant in the combination arm, the study treatment end date is the date of the last administration of the study treatment (for the combination arm, it will be the latest date between

29/94

the two study components; for the monotherapy arm it will be the last date of administration of tepotinib as monotherapy).

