Special cases: AEs may be split into multiple records if the toxicity grade changes (see Section 15.2.1 for more details). The end date of the previous record and the start date of the new record are expected to be the same. In the event that the month and year are indeed the same, but the day is missing, it will be imputed by 15. In case the imputed start date of the new record is after the end date of this same record, no imputation will be performed.

Prior osimertinib start and end dates

The following rules will be adopted to impute missing start or end dates:

- In case of partial start date with missing day, it will be imputed as the first day of the month.
- In case of partial end date with missing day, it will be imputed as the last day of the month or the day before the first dose of study treatment, whichever comes first.
- For both start and stop dates, if the month is missing or the date is completely missing, no imputation will be done.

Documented progressive disease

Incomplete dates for documented progressive disease as collected in the "Prior EGFR-TKI Drug Therapies Details", "Prior Osimertinib Therapies Details" and "Prior Anti-Cancer Drug Therapies Details" eCRF pages will be imputed as follows:

- If the day is missing, it will be imputed to the first day of the month.
- If the month is missing or the date is completely missing, no imputation will be done.

Previous and concomitant medication/procedure

For identification of previous or concomitant medications/procedures by period, no formal imputation will be performed on missing or incomplete dates. Rules presented in Table 4 and Table 5 will be used to define if a medication/procedure is considered as a previous, concomitant or both previous and concomitant medication/procedure.

If a medication/procedure could be allocated to both Period 1 and Period 2 due to missing start/stop dates, it will be allocated to Period 1. If a medication/procedure starts in Period 1 and continues in Period 2 it will also be allocated to Period 1.

End date of medication/procedure			Stopping rule	
Day	Month	Year		
UNK	UNK	UNK	After treatment start (ongoing)	
UNK	UNK	< Treatment start (year)	Before treatment start	
UNK	UNK	\geq Treatment start (year)	After treatment start	
UNK	< Treatment start (month and year)		Before treatment start	
UNK	\geq Treatment start (month and year)		After treatment start	
< Treatment start (complete date)		(complete date)	Before treatment start	

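### Does osimertinib taken up to the day before Cycle 1 Day 1 undermine the single-dose osimertinib results in the PK analysis?

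*SAP*

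**What the plan says.** SAP 16.1.2 obtains accumulation ratios for AUCtau and Cmax, for both drugs and their metabolites, "by dividing the values obtained after multiple dose (i.e., on Cycle 1 Day 15) by the values obtained after single dose" on Cycle 1 Day 1. Day 1 also supplies t_lag and the single-dose metabolite-to-parent ratio. These parameters are derived only for the rich-sampling participants, who are those in the safety run-in.

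On osimertinib before Day 1, Protocol 4.1 says that MET-positive participants who progressed on it "are recommended to continue treatment with osimertinib beyond progression, at the discretion of the Investigators". Protocol 4.2 gives the same advice, and Appendix 2 words it as what participants "should continue with the EGFR TKI beyond progression, until they either receive the experimental treatment as defined in this study". No entry criterion in Protocol 5.1 or 5.2 asks for an osimertinib-free interval.

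SAP 8.1 deals with carry-over in its definition of the PK analysis set. Osimertinib concentrations, parameters or both are excluded when there is "a change in scheduled osimertinib dose which can affect osimertinib PK (e.g., inadequate washout of prior osimertinib treatment", with missed doses as the second example. The same section admits only PK data free of factors that would put their validity in doubt, and adds: "All PK summaries will be based on the PKAS population".

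**The concern.** A participant who took osimertinib the day before Cycle 1 Day 1 is not receiving a first dose that day. The Day 1 profile then contains drug from earlier doses, the accumulation ratio is pulled towards 1 whatever the true accumulation, t_lag loses its meaning, and the Day 1 metabolite ratio is not a single-dose value. SAP 5 lists the single-dose osimertinib profile under a secondary PK objective, so the label matters.

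The exclusion in SAP 8.1 seems to leave the question open. Its trigger is a change in scheduled dose, and daily dosing continued unchanged is not obviously a change. If the exclusion is applied to concentrations, a second worry follows. Under Protocol 8.5 osimertinib is sampled at the tepotinib time points, so the Day 1 pre-dose sample is the only planned osimertinib value before tepotinib starts. Protocol 2.3 says the run-in sampling should show each drug's exposure in the presence of the other, and that value could drop out of the summaries.

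**Working it through.** **Inputs.** The dosing interval is 24 h and the comparison is Day 15 with Day 1 (SAP 16.1.2). The documents give no osimertinib half-life, so 24, 48 and 72 h are assumptions used for scale. The model is linear with one exponential, the daily dose is unchanged, and tepotinib has no effect on osimertinib. Let r = 2^(−24/half-life), which gives 0.500, 0.707 and 0.794. Let k be the number of days from the last earlier dose (taken at steady state) to Day 1, so k = 1 means no gap.

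**Formulas**, with AUCtau as a fraction of steady state:
- Day 1: 1 − r + r^k
- Day 15: 1 − r^15 + r^(k+14)
- Ratio for a true first dose: (1 − r^15)/(1 − r)

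**Results**

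| | 24 h | 48 h | 72 h |
|---|---|---|---|
| True first dose | 2.00 | 3.40 | 4.70 |
| No gap (k = 1) | 1.00 | 1.00 | 1.00 |
| Last dose 3 days before (k = 3) | 1.60 | 1.54 | 1.40 |
| Carry-over share of Day 1 AUCtau, k = 1 | 50% | 71% | 79% |

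With k = 1, Day 1 is 1 − r + r = 1 and Day 15 is 1 − r^15 + r^15 = 1, so the ratio is 1 at any half-life. That holds only if tepotinib leaves osimertinib exposure unchanged. If it does not, a continuing participant's ratio reflects the interaction and need not be 1.

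**Do such values reach a summary under the plan as written?**
1. Full continuation is the extreme case of inadequate washout, which SAP 8.1 gives as an example of what to exclude.
2. Apart from that clause, carry-over into a profile labelled single dose is plainly a factor that puts its validity in doubt. SAP 8.1 bars such data without requiring any change of dose.
3. Summaries use the PK analysis set only, and exclusions are settled at a data review meeting before lock (Protocol 9.3).
4. Excluded data are flagged with the reason, and parameters are listed for everyone with enough concentrations (SAP 16.1.1 and 16.1.2).

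**Must the pre-dose value be lost?** No. SAP 8.1 lets the exclusion fall on concentrations, on parameters or on both. The team can withhold the Day 1 ratio, t_lag and metabolite ratio and keep the pre-dose concentration. If that is excluded too, it is still listed.

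**How many participants?** The safety monitoring committee evaluated six run-in participants (Protocol 4.3). Some may have entered under protocol version 1.0: Protocol 9.4.1 checks run-in participants against the version 2 criterion of progression on first-line osimertinib, and SAP 11.5 mentions a prior EGFR-TKI form used only under version 1.0. A participant whose last inhibitor was not osimertinib would have a true first dose on Day 1. The number of continuing participants among those richly sampled is unknown and may be zero.

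**Would an added pre-dose comparison gain much?** The Day 15/Day 1 pre-dose ratio without interaction is (1 − r^14 + r^(k+13))/r^(k−1). With no gap it is 1.00. With one missed day (k = 2) it is 2.00, 1.41 and 1.25 for the three half-lives. A 6 h error in the clock time of the last pre-study dose shifts the Day 1 value by 2^(6/half-life), or 1.19, 1.09 and 1.06. An uncontrolled ratio in so few people, this sensitive to dosing history, adds little to the listed values.

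**The case for a change.** The best case for a change is textual. The lead-in of the washout clause speaks of a changed dose, adequate washout is not defined, and AZD5104 is not named. The compliance condition in SAP 8.1 does reach back to days before the PK measurement, but it concerns study treatment, and in SAP 9.2 "the study treatment start date is the date of first administration of the study treatment", so earlier osimertinib is not plainly within it. A partial end date for prior osimertinib is also unsafe for judging a gap: under SAP 9.9 "it will be imputed as the last day of the month or the day before the first dose of study treatment, whichever comes first", which can turn an unknown day into no gap. If the run-in mixes first-dose and continuing participants, one pooled ratio averages different quantities.

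The wording criticism stands as a drafting slip. Reading it so that no washout at all escapes a clause about inadequate washout defeats the clause's own example, and the validity condition would still apply. AZD5104 is formed from osimertinib, so an analyst who drops one Day 1 ratio for carry-over will drop the other. The date rule need not be relied on, because the Day 1 pre-dose sample measures carry-over directly. A pooled mixture arises only if the exclusion is not applied. The missing cut-off is a real gap, but it is a judgement for the data review meeting, where a handful of profiles can be examined one by one.

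**Conclusion.** No change follows. The single-dose label is wrong for any participant who continued osimertinib up to Day 1, and the distortion would be large for that person: a ratio of 1.00 instead of 2.0 to 4.7 under the assumed half-lives, linear PK, an unchanged dose and no interaction. The plan already has the means to keep such values out of the summaries, through the washout example, the validity condition and the restriction of summaries to the PK analysis set. It also keeps them visible in listings. What remains is an awkward lead-in and an unstated cut-off, which a PK analyst fills sensibly before lock.

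The reach is small. The derived ratios concern run-in participants only, in numbers the documents do not give. The accumulation ratio is not a named endpoint, and SAP 16.1.2 plans no PK hypotheses. Response, safety, tepotinib PK and Day 15 osimertinib parameters do not depend on it. This conclusion assumes that SAP 8.1 is applied as its washout example intends; it would not hold if Day 1 profiles with measurable pre-dose osimertinib were summarised as single-dose data.
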